**Secondary Outcome Measures:**

3. Pain score on the visual analogue scale [Time Frame: 10 days post-surgery], many patient reported outcomes like the number of times the bond failure take place, surgical time, pain associated with surgery will be assessed. (Annexure 3)

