**OUTCOME: Annexure 1;1**  
**Oral Health Impact Profile Questionnaire (OHIP-14)**  
**(Pre-treatment)**

S.no	Questions	Score (Tick any one)					
		Very Often	Fairly Often	Occasionally	Hardly ever	Never	Don't know
1.	Have you had trouble pronouncing any words because of problems with your teeth or mouth?						
2.	Have you felt that your sense of taste has worsened because of problems with your teeth or mouth?						
3.	Have you had painful aching in your mouth?						
4.	Have you found it uncomfortable to eat any foods because of problems with your teeth or mouth?						
5.	Have you been self-conscious because of your teeth or mouth?						
6.	Have you felt tense because of problems with your teeth or mouth?						
7.	Has been your diet been unsatisfactory because of problems with your teeth of mouth?						
8.	Have you had to interrupt meals because of problems with your teeth or mouth?						
9.	Have you found it difficult to relax because of problems with your teeth or mouth?						
10.	Have you been a bit embarrassed because of problems with your teeth or mouth?						
11.	Have you been a bit irritable with other people because of problems with your teeth or mouth?						
12.	Have you had difficulty doing your usual jobs because of problems with your teeth or mouth?						
13.	Have you felt that life in general was less satisfying because of problems with your teeth or mouth?						
14.	Have you been totally unable to function because of problems with your teeth or mouth?						

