**Annexure 1;3**

**Oral Health related Quality of life Questionnaire**  
**(24hrs after surgery)**

How much trouble you have with your teeth or mouth?

S.no	Questions	Score (Tick any one)				
		No trouble	A little trouble	Some trouble	Quite a lot trouble	Lots of trouble
1.	Eating/chewing foods you want					
2.	Opening your mouth wide					
3.	Sleeping					
4.	Talking to people so that they can understand you					
5.	Going about your everyday routine					
6.	Taking part in your social life					
7.	Taking part in sports					
8.	Swelling of your cheeks					
9.	Bruising					
10.	Bleeding					
11.	Nausea					
12.	Bad taste / bad breath					
13.	Food collecting in the hole after the teeth were pulled					
14.	Rate the worst pain you have felt in your teeth, mouth and face during past 24 hrs.	1	2	3	4	5

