**Annexure 1;4**  
**Oral Health related Quality of life Questionnaire**  
**(Ten days after surgery)**

How much trouble you have with your teeth or mouth?

S.no	Questions	Score (Tick any one)				
		No trouble	A little trouble	Some trouble	Quite a lot trouble	Lots of trouble
1.	Eating/chewing foods you want					
2.	Opening your mouth wide					
3.	Sleeping					
4.	Talking to people so that they can understand you					
5.	Going about your everyday routine					
6.	Taking part in your social life					
7.	Taking part in sports					
8.	Swelling of your cheeks					
9.	Bruising					
10.	Bleeding					
11.	Nausea					
12.	Bad taste / bad breath					
13.	Food collecting in the hole after the teeth were pulled					
14.	Rate the worst pain you have felt in your teeth, mouth and face during past 24 hrs.	1	2	3	4	5
15.	Are you still taking any pain killers? (yes/no)					
16.	If yes, How many days you took and frequency					

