### **Operator's measure of surgical ease (Annexure 3)**

Group (open/closed):

S.NO.	QUESTION	
1.	Actual surgical time- from incision to last suture	
2.	Difficulties felt by Operator	
3.	Number of times flap was raised	
4.	No of times button debonded	
5.	Duration of traction phase till alignment of canine	

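### The secondary pain outcome is stated as a visual analogue scale at 10 days, but the form cited for it has no pain item and no form shown carries such a scale

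*Protocol*

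**What the plan says.** The section Secondary Outcome Measures opens with "Pain score on the visual analogue scale [Time Frame: 10 days post-surgery". The same sentence goes on to bond failures, then "surgical time, pain associated with surgery will be assessed. (Annexure 3", so a single annexure is cited for pain, bond failure and surgical time together.

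Annexure 3 is headed as the operator's "measure of surgical ease (Annexure 3". It includes "Actual surgical time- from incision to last suture" as item 1 and "No of times button debonded" as item 4.

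Patients rate pain on the Annexure 1 questionnaires. Item 3 of both OHIP-14 forms (pre- and post-treatment) asks "Have you had painful aching in your mouth". Item 14 of the 24-hour form (Annexure 1;3) asks "Rate the worst pain you have felt in your teeth, mouth and face during past 24 hrs", with answers 1 to 5. The form headed "Ten days after surgery" (Annexure 1;4) repeats that item with the same five answers. The section Primary Outcome Measures assigns Annexure 1 to oral-health quality of life.

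**The concern.** A secondary outcome needs an instrument, a time and a place where it is recorded. Here the protocol names all three, and they do not fit together: the form cited is the operator's and does not ask about pain, while the day-10 form that does ask about pain uses a different scale and is not cited.

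The third objective is to compare patient-reported outcomes between the open and closed techniques, and pain is one of the few that the protocol names. If site staff complete exactly the forms shown, the trial ends with no VAS score. The report would then have to put a five-level item in place of the stated scale after the data are in. A VAS not taken at day 10 cannot be recovered later. The only other route is a VAS on a sheet that the protocol neither shows nor cites.

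**Working it through.** No formula applies. The check is a count across the forms, set against the outcome statement.

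**Step 1: the form that is cited.** The five items of Annexure 3 are surgical time, difficulties felt by the operator, number of flap raisings, number of button debonds, and duration of traction. Pain items: 0 of 5. Of the three kinds of outcome for which the form is cited, it holds two (surgical time in item 1, bond failure in item 4) and lacks the third (pain).

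**Step 2: all forms shown.** There are seven annexure forms (1;1, 1;2, 1;3, 1;4, 2, 3, 4) and a baseline sheet.

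| Form | When | Pain rating | Scale |
|---|---|---|---|
| Annexure 1;1 | pre-treatment | item 3 | frequency of aching |
| Annexure 1;2 | post-treatment | item 3 | frequency of aching |
| Annexure 1;3 | 24 hours after surgery | item 14 | 1 to 5, worst in past 24 hours |
| Annexure 1;4 | ten days after surgery | item 14 | 1 to 5, worst in past 24 hours |
| Annexures 2, 3, 4 and baseline sheet | various | none | none |

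Four of the seven annexure forms hold a pain rating: two frequency items and two 1-to-5 ratings. One of the four is at day 10. None is a VAS. Items 15 and 16 of Annexure 1;4 ask about painkiller use, which is not a pain score.

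**Step 3: match to the stated outcome.**
- Time: Annexure 1;4 fits day 10.
- Scale: no form shown fits.
- Citation: Annexure 3 does not fit, and Annexure 1;4 is not cited for pain.

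**Step 4: a second reading of the time frame.** The wording could mean the period up to day 10 rather than day 10 itself. The 24-hour rating would then also fall inside it. That item is also a 1-to-5 rating in Annexure 1, so neither the scale nor the citation is repaired.

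**Step 5: surgical time.** Annexure 3 uses one rule for both groups, ending at the last suture. The background description of the open technique has a mucosal window covered by a dressing, and the treatment section has a pack; neither mentions a suture. For the closed technique, the background mentions suturing, but the treatment section does not.

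**The case against.** **It is only a label.** Patients do rate their worst pain at ten days, and the authors may simply be calling item 14 a VAS. Its printed layout cannot be verified, because tables suffer when a PDF is read by a program. A protocol also need not reproduce every form, and some pages of the public copy are missing, so a VAS sheet may exist. Part of this stands: the finding covers only the forms shown, as read. What it does not rescue is the citation. Annexure 3 is shown, and it has no pain item whatever the other pages contain. Five numbered answers are also not what the words visual analogue scale describe.

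**Stronger readings that the documents do not support.** A reader might infer that day-10 pain is not collected at all; item 14 of Annexure 1;4 shows otherwise. A reader might also infer that surgical time has no end in the open arm because no suture is placed there. That is an argument from silence. The open-technique text does not exclude sutures, and the closed-technique treatment section omits them too, although the background says that the closed technique is sutured. It is a point to clarify, not a demonstrated error. The documents give no durations, so no effect on the comparison can be computed.

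**It touches only secondary outcomes.** True. The sample size, the randomisation and the primary outcome measures do not depend on it.

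**Conclusion.** The point holds as a mismatch of instrument and form, not as missing pain data. The stated secondary outcome cannot be obtained from the form cited for it (0 of 5 items), and no form shown carries the stated scale (0 of 7 annexure forms, 0 on the baseline sheet). One day-10 pain rating exists. It has five levels and sits in a questionnaire set assigned to a primary outcome. Letting it stand in unannounced would make one item serve a primary and a secondary outcome without the protocol saying so.

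This should be corrected before day-10 data are collected. It is more than a clerical slip, because the VAS score is lost if nobody takes it, but it does not undermine the primary outcomes. The conclusion assumes that the forms in the public copy are the ones in use and that item 14 appears on paper as five numbered answers.

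The end point of surgical time is a minor clarification only.

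**What to change.** **Preferred.** Add one VAS pain line to the ten-day patient form (Annexure 1;4). Under Secondary Outcome Measures, cite that form for pain and cite Annexure 3 only for operator-recorded outcomes. While editing, state which debond count is meant by bond failure: Annexure 3 item 4 counts button debonds and Annexure 2 item 7 counts bracket debonds. The cost is one line on an existing form and a corrected citation.

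**Alternative.** Name item 14 of Annexure 1;4 as the pain outcome and delete the reference to a visual analogue scale. No form changes. The cost is an outcome with only five levels, taken from an item that also belongs to the primary questionnaire; the protocol should state both.

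**Clarification.** State one end-of-procedure time point for surgical time that applies in both arms. This concerns measurement only and changes no procedure. If the chosen point counts pack placement in the open arm's time, the report should say so, because that choice enters the between-arm difference.

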**4. EXPERIMENTAL SCHEDULE & OUTCOME FOR 3 YEARS:**

Time in Months	1-2m	2-12m	12-30m	30-36m
Training of Research Associate and enrollment of patients				

Implementation of project and treatment phase				
Data Analysis and compilation of results				

**5. SHADOW PRICING OF PROPOSED STUDY & MODALITIES:** This is a routine fixed orthodontic procedure in Dept. of Orthodontics, Faculty of Dentistry, Jamia Millia Islamia and materials related to this project will be provided by the institute.

**6. SCIENTIFIC IMPACT OF PROPOSED STUDY:** According to present literature, there is no evidence to support either the open or the closed technique for exposing palatally ectopic canines to be clinically superior in terms of dental health, aesthetics, economics and patient factors. There is a high need for randomized clinical trials on this subject, the current literature provides very weak evidence. Current evidence gaps need to be filled. Our study aims at providing evidence as to which technique should be used to expose palatally impacted canines, open or closed. It will take into consideration the primary outcomes like periodontal health of the disimpacted teeth as well as the secondary outcomes that is the patient reported outcomes including patient comfort and aesthetics. This study might provide some good evidence which could help the surgeon and orthodontist to decide the suitable approach for a particular case.

#### **7. INSTITUTIONAL ETHICAL COMMITTEE CLEARANCE:**

The project has received approval from Institutional ethical committee (IEC), Jamia Millia Islamia, New Delhi.

#### **8. MY SPECIFIC FUNCTION & ROLE IN THE PROPOSED STUDY:**

After allocation of patients in both the groups, being an investigator, my role shall be clinical intervention from bonding the brackets to orthodontic dis-impaction of impacted canines to its normal position. Being a clinical research project, it will be

help in practicing both clinical, and research analysis. It will be a team effort i hope to contribute to the practice of evidence based dentistry through this project. By performing it to best of my abilities and minimizing bias.

**OUTCOME: Annexure 1;1**  
**Oral Health Impact Profile Questionnaire (OHIP-14)**  
**(Pre-treatment)**

S.no	Questions	Score (Tick any one)					
		Very Often	Fairly Often	Occasionally	Hardly ever	Never	Don't know
1.	Have you had trouble pronouncing any words because of problems with your teeth or mouth?						
2.	Have you felt that your sense of taste has worsened because of problems with your teeth or mouth?						
3.	Have you had painful aching in your mouth?						
4.	Have you found it uncomfortable to eat any foods because of problems with your teeth or mouth?						
5.	Have you been self-conscious because of your teeth or mouth?						
6.	Have you felt tense because of problems with your teeth or mouth?						
7.	Has been your diet been unsatisfactory because of problems with your teeth of mouth?						
8.	Have you had to interrupt meals because of problems with your teeth or mouth?						
9.	Have you found it difficult to relax because of problems with your teeth or mouth?						
10.	Have you been a bit embarrassed because of problems with your teeth or mouth?						
11.	Have you been a bit irritable with other people because of problems with your teeth or mouth?						
12.	Have you had difficulty doing your usual jobs because of problems with your teeth or mouth?						
13.	Have you felt that life in general was less satisfying because of problems with your teeth or mouth?						
14.	Have you been totally unable to function because of problems with your teeth or mouth?						

**Annexure 1;2**  
**Oral Health Impact Profile Questionnaire (OHIP-14)**  
**(Post-treatment)**

S.no	Questions	Score (Tick any one)					
		Very Often	Fairly Often	Occasionally	Hardly ever	Never	Don't know
1.	Have you had trouble pronouncing any words because of problems with your teeth or mouth?						
2.	Have you felt that your sense of taste has worsened because of problems with your teeth or mouth?						
3.	Have you had painful aching in your mouth?						
4.	Have you found it uncomfortable to eat any foods because of problems with your teeth or mouth?						
5.	Have you been self-conscious because of your teeth or mouth?						
6.	Have you felt tense because of problems with your teeth or mouth?						
7.	Has been your diet been unsatisfactory because of problems with your teeth of mouth?						
8.	Have you had to interrupt meals because of problems with your teeth or mouth?						
9.	Have you found it difficult to relax because of problems with your teeth or mouth?						
10.	Have you been a bit embarrassed because of problems with your teeth or mouth?						
11.	Have you been a bit irritable with other people because of problems with your teeth or mouth?						
12.	Have you had difficulty doing your usual jobs because of problems with your teeth or mouth?						
13.	Have you felt that life in general was less satisfying because of problems with your teeth or mouth?						
14.	Have you been totally unable to function because of problems with your teeth or mouth?						

**Annexure 1;3**

**Oral Health related Quality of life Questionnaire**  
**(24hrs after surgery)**

How much trouble you have with your teeth or mouth?

S.no	Questions	Score (Tick any one)				
		No trouble	A little trouble	Some trouble	Quite a lot trouble	Lots of trouble
1.	Eating/chewing foods you want					
2.	Opening your mouth wide					
3.	Sleeping					
4.	Talking to people so that they can understand you					
5.	Going about your everyday routine					
6.	Taking part in your social life					
7.	Taking part in sports					
8.	Swelling of your cheeks					
9.	Bruising					
10.	Bleeding					
11.	Nausea					
12.	Bad taste / bad breath					
13.	Food collecting in the hole after the teeth were pulled					
14.	Rate the worst pain you have felt in your teeth, mouth and face during past 24 hrs.	1	2	3	4	5

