**OBJECTIVES:**

1. To assess oral health related quality of life in patients undergoing canine disimpaction through Questionnaire.
2. To assess periodontal outcomes between the open and closed surgical techniques.
3. To assess whether there are differences in patient reported outcomes between the open and closed surgical techniques.

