### **Treatment Protocol:**

The orthodontic treatment will be done by single orthodontist who will follow a strict protocol as follows:

1. Initial orthodontic alignment will be aimed at creating space in the maxillary arch with fixed appliance therapy (0.022 slot) .The surgical procedure will be done after reaching a full size wire of 19X25 S.S with open coil spring to maintain space for the permanent canine. Anchorage preparation will also be done with the help of TPA.

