**Primary Outcome Measures:**

1. Oral health based Quality of life of patients undergoing canine disimpaction will be accessed by questionnaire. (Annexure 1)
2. Measurement of width of attached gingiva. Measures which assess the periodontal outcome like crown length, gingival recession, bone will be assessed. (Annexure 2).

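### The post-surgical trouble questionnaire has no pre-surgical administration, so surgical trouble cannot be separated from existing appliance trouble within patients; the open-versus-closed comparison is not biased

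*Protocol*

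**What the plan says.** Objective 1 is "To assess oral health related quality of life in patients undergoing canine disimpaction through Questionnaire". It names no contrast between the arms. Objective 3 does: "To assess whether there are differences in patient reported outcomes between the open and closed surgical techniques". Item 1 of Primary Outcome Measures makes quality of life primary and points to Annexure 1: "Oral health based Quality of life of patients undergoing canine disimpaction will be accessed by questionnaire".

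Annexure 1 holds four forms on two instruments:

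- **OHIP-14**, before treatment (Annexure 1;1) and after treatment (Annexure 1;2). It asks how often a problem occurs, for example "Have you had trouble pronouncing any words because of problems with your teeth or mouth", with answers from very often to never plus a don't-know option.
- **Trouble form**, at 24 hours (Annexure 1;3) and ten days (Annexure 1;4) after surgery. The stem is "How much trouble you have with your teeth or mouth", graded from no trouble to lots of trouble, with worst pain rated 1 to 5. The ten-day form adds two painkiller items.

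Item 1 of Treatment Protocol sets the order of treatment: "The surgical procedure will be done after reaching a full size wire of 19X25 S.S with open coil spring to maintain space". Anchorage with a TPA is prepared in the same phase. The Baseline Data sheet has no field for quality of life or pain.

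**The concern.** A form completed 24 hours or ten days after an operation invites the reading that its scores show what the operation did. That reading needs a measurement on the same scale shortly before the operation, and none is scheduled. By the time of surgery the patient already wears a fixed upper appliance on a heavy wire, with a spring and a palatal arch. Difficulty eating or talking, a bad taste and aching may all be present before the surgeon begins, and the stem does not ask the patient to set them aside.

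At stake is the description of quality of life around surgery, which is part of a primary outcome. The ambiguity is likely to be greatest at ten days, if acute surgical effects have eased while the appliance remains: a residual score could be slow recovery or simply the appliance. The gap lies in the data-collection forms, so an analysis plan cannot close it afterwards.

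**Working it through.** **1. What is measured, and when**

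| Moment | OHIP-14 | Trouble form |
|---|---|---|
| Before treatment | yes | no |
| After alignment, before surgery | no | no |
| 24 hours after surgery | no | yes |
| Ten days after surgery | no | yes |
| After treatment | yes | no |

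The trouble form is given 0 times before surgery and 2 times after. Neither instrument is given between the fitting of the appliance and surgery. The OHIP-14 change spans the whole treatment. The contralateral canine, named as control under Study design, can be a control for a tooth but not for a patient-level score.

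**2. Which items are affected**

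- General, 9 items: eating, mouth opening, sleeping, talking, routine, social life, sports, bad taste or breath, worst pain (items 1 to 7, 12 and 14).
- Largely surgery-specific, 5 items: swelling, bruising, bleeding, nausea, food in the hole (items 8 to 11 and 13).

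**3. Effect on the level and on the contrast**

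Write a post-surgery score as appliance trouble A plus surgical trouble S plus error. Illustrative values, all assumed: mean A = 1.0 in both arms, mean S = 0.5 in one arm and 1.0 in the other.

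- Pooled level: 1.0 + (0.5 + 1.0)/2 = 1.75, against a mean surgical effect of 0.75. The whole of A is absorbed.
- Between arms: (1.0 + 1.0) − (1.0 + 0.5) = 0.50, the true difference. A cancels.

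A simulation of 20,000 trials with 20 per arm (SD 0.7 for A and for error) gave 1.75 and 0.50.

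**4. Precision of the between-arm comparison**

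The protocol gives no sample-size figure for quality of life. Its total of 40 is based on clinical attachment and enters here only as the number of patients. (That figure does not follow from its own two-sided inputs: 2 × (1.96 + 0.84)² × (0.61/0.5)² gives 24 per arm, 48 in all. This is a separate matter, and nothing below rests on it.)

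Let r be the correlation between pre- and post-surgical scores, for which the documents give no value. Covariate adjustment multiplies the variance by 1 − r², ignoring the one degree of freedom spent. The equivalent sample is 40/(1 − r²). The difference detectable with 80% power at two-sided 0.05 is (1.96 + 0.84) × √(2/20) × √(1 − r²) SD, by the normal approximation.

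| Assumed r | Variance cut | Equivalent patients | Detectable difference (SD) |
|---|---|---|---|
| 0 | 0% | 40 | 0.89 |
| 0.1 | 1% | 40.4 | 0.88 |
| 0.2 | 4% | 41.7 | 0.87 |
| 0.3 | 9% | 44.0 | 0.85 |
| 0.5 | 25% | 53.3 | 0.77 |
| 0.6 | 36% | 62.5 | 0.71 |

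**The case against.** The strongest reply is that the protocol never promises an isolated effect of surgery. Its Background describes management as exposure together with a fixed appliance, so the appliance is part of disimpaction. Objective 1 asks only to assess quality of life during that process, and the paired OHIP-14 covers change over the whole treatment. This stands in part: the protocol does not contradict itself, and the gap is a design choice. But two forms timed from the operation will be read as describing its effect, and the data cannot support that reading on the general items.

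A reader might infer four stronger things, none of which the documents support:

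- **That the open-versus-closed comparison is biased.** Allocation is random, and a single orthodontist follows one pre-surgical protocol in both arms, so appliance trouble is equal in expectation. Chance imbalance is already reflected in the standard error.
- **That the whole appliance treatment precedes surgery.** Only initial alignment does; traction and finishing follow.
- **That every item is contaminated.** Five of the 14 are largely specific to surgery.
- **That the OHIP-14 is useless as a baseline.** It cannot be subtracted from a trouble score, but a covariate need not share the outcome's scale, and whether to adjust is commonly left to the analysis plan.

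Two further cautions hold. The correlation between settled appliance trouble and acute trouble at 24 hours may be close to zero, in which case almost no precision is gained. And a pre-surgical form would be completed after allocation: Randomization places allocation after consent, and section 8 places it before bracket bonding. No blinding of patients is described, so they may know their arm when they answer.

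**Conclusion.** The point holds for objective 1 and the nine general items: surgical trouble cannot be separated from existing appliance trouble, and no within-patient change across surgery can be formed. This follows from the forms and the treatment sequence and needs no numerical assumption. How much of the score is appliance trouble is unknown; the 1.75 against 0.75 shows the mechanism and is not an estimate.

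For objective 3 the cost is limited to precision and a check of balance. The precision forgone ranges from nothing to a 36% cut in variance over an assumed correlation of 0 to 0.6, and the upper end should not be quoted alone. The change is worth making because a primary outcome is affected and a missed baseline cannot be recovered once a patient has been operated on.

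**What to change.** Give the nine general items, with the same wording and response scale, once at the pre-surgical visit, after alignment and before surgery. Then:

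1. Report change at 24 hours and ten days on those nine shared items only. A nine-item baseline cannot be subtracted from a 14-item score.
2. Report the five surgery-specific items as post-surgery levels.
3. Use the nine-item pre-surgical score as a covariate in the between-arm comparison, and report the unadjusted comparison alongside, because this baseline is taken after allocation from patients who may know their arm.

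The cost is one self-completed page, a few minutes per patient and a line in the analysis. If the form is not added, restrict conclusions from the 24-hour and ten-day forms to the contrast between open and closed exposure, and say that their absolute levels include appliance trouble.
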